The original adult short form (7a) was constructed by the domain team with a focus on representing the range of the trait and also representing the content of the item bank. Domain experts reviewed short forms to give input on the relevance of each item. Each domain group worked independently

and the original short forms are 6-10 items long depending on the domain. Psychometric properties and clinical input were both used and likely varied in importance across domains.

Extended Activities-Specific Balance Confidence (ABC) Scale

The ABC Scale (Lajoie 2004) is a self-administered questionnaire that asks the patient to rate his or her confidence in performing various ambulatory activities on a scale from 0% (no confidence) to 100% (complete confidence) without losing balance or becoming unsteady. Scores for each of the 16 items will be collected and an average percentage calculated, with scores <67 indicating an increased risk of falling (Miller et al., 2003/2004).

5 items of interest were added to gauge the impact of the reported increase in proprioception in earlier models of the Revo-M on balance confidence.

This test was selected since it measures patient perceived balance confidence, and is expected to help assess the impact of the new foot.

Prosthetic Limb Users Survey-M (PLUS-M)

The PLUS-M is a valid and reliable self-reported measure for the mobility of adults with lower limb amputations. PLUS-M asks about the subject's ability to perform simple and complex tasks. This questionnaire asks about the current timeframe for the patient. High PLUS-M scores correspond with greater mobility (Hafner et al., 2016).

EQ-5D-5L

The EQ-5D-5L is a standardized measure of health status developed by the EuroQol group, applicable to a wide range of health conditions and treatments. It has widespread currency outside the profession. It is often referred to as a quality of life questionnaire.

The EQ-5D-5L, is a very simple measure which subjects complete at the start and end of treatment. Its name means 'EuroQol – 5 Dimensions – 5 Levels' and comprises five dimensions of health: mobility, ability to self-care, ability to undertake usual activities, pain and discomfort, and anxiety and depression. There are five options (levels) under each domain. Index scores will be computed whereby higher scores indicate higher quality of life.

PROMIS Pain Interference

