Outcome measures obtained after using the Revo-M foot for 8 weeks will be compared to baseline measures obtained using everyday feet with a 2-sided Wilcoxon matched pairs signed ranks test. The Hochberg method will be used to adjust alpha for the multiple primary effectiveness endpoints, thereby limiting the family-wise alpha to 0.05. In this method, p-values are ranked from highest to lowest for each primary endpoint tested. If the highest p-value is ≤ 0.05 , all null hypotheses will be rejected and no further adjustment will be made. If, however, the highest p-value is > 0.05 , alpha will be adjusted to 0.025 (alpha/2). The remaining p-value must be ≤ 0.025 in order to be statistically significant. Adjustment of alpha will continue in this manner for all primary effectiveness endpoints. Two-tailed p-values \leq the Hochberg adjusted alpha will indicate statistical significance. Primary efficacy endpoints (2 endpoints) will be considered one family and secondary efficacy endpoints (3 endpoints) will be considered a second separate family. The Hochberg method will not be applied to exploratory endpoints.

If the observed p-value is \leq the Hochberg adjusted critical value, the difference will be regarded as statistically significant. Because this is a randomized crossover study, the Revo-M may be either the first or second new foot used after baseline measures with the everyday feet. It is important to assess whether differences between Revo-M and everyday feet scores are influenced by the order in which the new feet are assigned. To evaluate this a difference score will be computed by subtracting everyday feet scores from Revo-M scores. Difference scores for subjects receiving the Revo-M foot first will be compared to those of subjects who received the Revo-M foot second (after a comparative foot) using Wilcoxon's rank sum test. A resulting p-value ≤ 0.05 will indicate that differences in the specified outcome measure may depend on the order in which the Revo-M was

assigned and not simply due to the Revo-M itself. Interpretation of differences between Revo-M and everyday feet scores will be modified accordingly.

Primary Efficacy Endpoints

Primary Efficacy Endpoint #1: Perception of mobility as measured by the PLUS-M. It is hypothesized that PLUS-M scores will be higher for subjects when they are using the Revo-M compared to their everyday feet. In statistical terms the null and alternative hypotheses are as follows:

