Secondary Efficacy Endpoint #1: Level of walking endurance as measured by the distance walked in the six-minute walk test (6MWT) and the perceived exertion (RPE) measured by Borg CR100. No hypothesis will be tested. Instead, the percentage of subjects (along with the exact 95% binomial confidence interval) with either a clinically meaningful improvement in the distance walked in the six minute walk test or a clinically meaningful decrease in the rating of perceived exertion (RPE) while wearing the Revo-M foot compared to the everyday foot will be computed. A clinically-significant improvement in the 6MWT is defined as a change in distance of greater than 45 meters [Resnik 2011]. A clinically-significant improvement in the RPE is defined as a change greater than 10 points [Ries 2005].

Secondary Efficacy Endpoint #2: Perception of balance confidence as measured by the extended Activities-specific Balance Confidence (ABC) Scale. It is hypothesized that ABC scores will be higher for subjects when they are using the Revo-M compared to their everyday feet. In statistical terms the null and alternative hypotheses are as follows:

$$H_0: \mu_{\text{Revo-M}} \leq \mu_{\text{Everyday}}$$

$$H_A: \mu_{\text{Revo-M}} > \mu_{\text{Everyday}}$$

Where H_0 is the null hypothesis, $\mu_{\text{Revo-M}}$ is the mean ABC score using the Revo-M, μ_{Everyday} is the mean ABC score using the everyday feet and H_A is the alternative hypothesis indicating that balance confidence as measured by the ABC scale is greater for Revo-M than for everyday feet.

The hypothesis will be tested using a 2-sided Wilcoxon matched pairs signed ranks test. If the observed p-value is \leq the Hochberg adjusted critical value and the mean of PLUS-M scores using the Revo-M foot is greater than PLUS-M scores using the everyday feet, the null hypothesis will be rejected in favor of the alternative hypothesis and the superiority of the Revo-M will be supported.

Secondary Efficacy Endpoint #3: Level of functional satisfaction as measured by the TAPES Functional Satisfaction (TAPES-FUN) subscale. It is hypothesized that TAPES-FUN scores will be higher for subjects when they are using the Revo-M compared to their everyday feet. In statistical terms the null and alternative hypotheses are as follows:

$$H_0: \mu_{\text{Revo-M}} \leq \mu_{\text{Everyday}}$$

$$H_A: \mu_{\text{Revo-M}} > \mu_{\text{Everyday}}$$

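### The plan does not settle whether the ABC score tested as secondary endpoint #2 averages 16 items or 21; it should be fixed as the 16-item mean

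*Combined protocol and SAP*

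**What the plan says.** The Clinical Study Summary, the Secondary Efficacy Objectives, Table 2 and Secondary Efficacy Endpoint #2 all name the extended form of the scale. The endpoint is "Perception of balance confidence as measured by the extended Activities-specific Balance Confidence (ABC) Scale".

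The only scoring rule is in Clinical Tests & Measures, under the Extended ABC Scale: "Scores for each of the 16 items will be collected and an average percentage calculated, with scores <67 indicating an increased risk of falling". The next paragraph states "5 items of interest were added to gauge the impact of the reported increase in proprioception in earlier models of the Revo-M", and the sentence ends by naming balance confidence as what the impact is on. No rule says how the five items are scored, or whether they enter the average.

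Secondary Efficacy Endpoint #2 defines the tested quantity only by the words "is the mean ABC score using the Revo-M" and its counterpart for the everyday feet. The test is stated as "The hypothesis will be tested using a 2-sided Wilcoxon matched pairs signed ranks test", and a favourable result allows the conclusion that Revo-M is superior. On multiplicity, the Hypothesis section says "secondary efficacy endpoints (3 endpoints) will be considered a second separate family".

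**The concern.** The endpoint's name points to 21 items and the scoring sentence points to 16. Table 2 schedules the extended questionnaire at Visits 2 to 5, so both scores can be computed for every Revo-M versus everyday-foot comparison. With no stated rule, an analyst could choose between them with the results in hand, inside a family where alpha is meant to be controlled.

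The choice is not neutral. The five items were added to look for an effect reported with earlier models of the test device. If they enter the mean, a change confined to them could be reported as superiority on the ABC.

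The ambiguity could also outlast this study. The section on interim analysis and adaptive design foresees a pivotal trial that reuses these subjects' data, is sized from the differences and SDs observed here, and is powered for secondary as well as primary objectives.

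**Working it through.** **The plan's own figures.** No effect size, SD or sample size is given for ABC, so there is no ABC figure to reproduce. The stated sizes of 22 (PLUS-M) and 21 (TAPES-AR) do reproduce, as the paired t-test n divided by the Wilcoxon efficiency 3/π: 21/(3/π) = 21.99 and 20/(3/π) = 20.94. This point does not affect them.

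**Inputs from the documents.** 16 scored items and 5 added items (Extended ABC Scale); minimum n = 24 (Sample Size); two-sided signed-rank test (Secondary Efficacy Endpoint #2); Hochberg within the secondary family (Hypothesis).

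**Assumed inputs, not in the documents.** SD of the paired ABC difference of 8 to 12 points; a rise d of 10, 15 or 20 points on the five items; no change on the 16 items; normal differences.

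**Step 1, weight and shift.** With M16 and M5 the means of the two item sets,

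M21 = (16 × M16 + 5 × M5) / 21.

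The added items carry 5/21 = 23.8%. If M16 does not change and M5 rises by d, M21 rises by 5d/21: 50/21 = 2.38, 75/21 = 3.57 and 100/21 = 4.76 points.

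**Step 2, how often the 21-item score would be significant.** Simulated at n = 24, with the SD applied to the 21-item difference:

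| Rise on the five items | Shift in 21-item mean | Significant at 0.05 (SD 12 to SD 8) | Significant at 0.025 (SD 12 to SD 8) |
|---|---|---|---|
| 10 | 2.4 | 15–27% | 9–18% |
| 15 | 3.6 | 28–52% | 18–42% |
| 20 | 4.8 | 44–77% | 34–68% |

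The last column matters because secondary endpoint #1 is not tested, so only ABC and TAPES-FUN yield p-values. If the TAPES-FUN p-value exceeds 0.05, Hochberg requires ABC to reach 0.025.

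**Step 3, a second model.** Giving each item set its own SD of 8 to 12, with correlation 0.3 to 0.9 between their changes, yields 15–35% for a 10-point rise and 46–88% for a 20-point rise at 0.05.

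**Step 4, the comparison.** If the 16-item mean is tested and has not truly changed, favourable significance at two-sided 0.05 occurs in about 2.4% of trials, whatever the five items do. If the five items do not move either, the 21-item score also stays at about 2.4%.

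**The case against.** The best defence is that the only scoring rule sits under the Extended ABC heading and averages 16 items. Read literally, the tested score is already the 16-item mean and none of the rates above arise. That reading is reasonable, but the endpoint text repeatedly names the extended scale and never refers back to the 16-item rule. The documents support an undefined score. They do not support a claim that the plan has chosen 21 items.

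A reader might infer four stronger things that the documents do not support:

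- **That the items were picked because earlier devices had moved them.** What was reported with earlier models is increased proprioception. Nothing says that these items, or any balance-confidence score, changed. Nor does the text say who added them, and the sentence ties them to balance confidence, which is the endpoint's own construct.
- **That the percentages are false-positive rates.** If the five items truly rise, the 21-item mean truly rises and rejecting its null is correct. The error would be to credit the result to the standard scale.
- **That the percentages predict this trial.** They rest on assumed SDs and shifts. No change on 16 items beside a 10 to 20 point rise on five is a deliberately stark case.
- **That fall-risk classification is distorted.** The cut at 67 appears only in the description of the scale, and no planned analysis uses it.

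It is also fair to say that this is a secondary endpoint without its own power calculation, in a feasibility study whose analysis is described as mainly descriptive. That limits the stakes. The plan nevertheless attaches a superiority conclusion and alpha control to this endpoint, so the score should be fixed in advance.

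**Conclusion.** The concern holds as a definitional gap with a real consequence. The documents do not settle whether secondary endpoint #2 averages 16 or 21 items. If 21 are used, 24% of the score comes from items added to gauge an effect reported with earlier models of the device, and a change confined to those items could be presented as ABC superiority. Under the assumptions in the first model, that would happen in roughly 15% to 77% of trials at alpha 0.05, and in 9% to 68% where Hochberg requires 0.025. The weight and the shifts in the mean are plain arithmetic; the percentages are illustrations only. If the 16-item mean is what is meant, the problem disappears once the plan says so.

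**What to change.** State in both the Extended ABC Scale section and Secondary Efficacy Endpoint #2 that the endpoint is the mean of the 16 ABC items, and that only this score is tested in the secondary Hochberg family. Report the five added items as a separate exploratory score, outside that family.

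Fixing 21 items in advance would also remove the choice after the fact. It would still leave a superiority statement about the ABC partly resting on items outside the 16-item score that the protocol describes, so 16 is the better choice.

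The same edit should correct the decision rule for this endpoint. Its direction condition is written as "the mean of PLUS-M scores using the Revo-M foot is greater than PLUS-M scores using the everyday feet", and it should refer to ABC scores.

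The cost is wording only, because the extended questionnaire is already scheduled at every relevant visit. The downside for the sponsor is that a benefit confined to the added items would no longer support an ABC superiority claim; it would appear as an exploratory finding.

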The study is planned to be divided into four periods as illustrated in Figure 4. The only clinical measures to occur from the beginning of Period I are the StepWatch, Patient Journal, and Socket Comfort Score. After enrollment, the subject will spend 8 weeks (+/-2 weeks) using their own energy storage and return foot. Informed consent, demographic information, general health information, and adverse events will be collected during this period. After enrollment, the subject will be randomized to Revo, Taleo (if a transfemoral amputee), or the Proflex XC (if a transtibial amputee).

Period II – Period IV

Baseline measures are taken just prior to Period II. After the first 8 week follow up, the subject will crossover to the second comparator. After the second 8 week follow up, the subject will crossover to control. During Period IV, assessments will be repeated as in baseline. Table 2 summarizes the assessments and order of events.

[figure not shown]

Figure 4 Study Periods and Visits

Table 2 Assessments by Period and Study Visit

Period I (Control)			Period II (Revo/ Comparative)	Period III (Revo/ Comparative)	Period IV (Control)
	Visit 1	Visit 2	Visit 3	Visit 4	Visit 5
Measurement	Enrollment	Baseline 8 ± 2 weeks	Period II Follow up 8 ± 2 weeks	Period III Follow up 8 ± 2 weeks	Period IV Follow up 8 ± 2 weeks
Demographics / General Health	X				
SCS	X	X	X	X	X
ABC (extended)		X	X	X	X
PLUS-M		X	X	X	X
PROMIS-F (7a)		X	X	X	X
TAPES-FUN + TAPES-AR		X	X	X	X
EQ-5D-5L		X	X	X	X
6 Minute Walk Test (incl. BORG RPE and continuous HR)		X	X	X	X
Foot Preference Questionnaire					X
Patient Journal (incl. Pain Interference)	X	X	X	X	X
Step Count*	X	X	X	X	X
Adverse Events	X	X	X	X	X
Fitting with prosthetic foot for subsequent Period		X	X	X	

* Subject is fitted with StepWatch at previous visit so that the data may be collected prior to the following visit, this process starts at enrollment

Objectives

Safety

Safety Objectives

1. To characterize all device-related adverse events, stumbles, and falls experienced by subjects in the study by frequency and severity.

Effectiveness

Primary Efficacy Objectives

1. To characterize perception of mobility as measured by the PLUS-M while wearing the Revo-M compared to the everyday feet.
2. To characterize the level of activity restrictions as measured by the Trinity Amputation and Prosthesis Experience Scales Activity Restrictions subscale (TAPES-AR) while wearing the Revo-M compared to the everyday feet.

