The fittings during Period II and Period III are determined at random and according to amputation level. Subjects will be randomized to start with either the Revo (regardless of amputation level) or the comparative foot: Taleo if TF or KD, Proflex XC if TT. After completing Period II with the assigned foot, subjects will cross over to be fit with either the Revo, if starting with the comparative foot or the comparative foot if starting with the Revo.

Fitting process for the Revo-M investigational foot

The Revo prosthetic foot has several components which have different mechanical characteristics to allow the foot to be tailored to the patient. Subjects will complete several walking trials to determine the optimal configuration.

Fitting process for the comparative feet: Taleo and ProFlex XC

The Taleo is customizable with heel wedges that come in three different stiffnesses (soft, medium and hard). The CPO may give the subjects the opportunity to try each wedge to determine which is best.

ProFlex XC does not have any customizable components, so no configuration process is required.

Home-use Periods

Subjects will have four home-use periods during the study approximately 8 weeks in duration as shown in Figure 4 above. Prior to each home-use period, subjects will be fitted with the assigned foot and be given a Patient Journal and a StepWatch activity monitor. The Patient Journals will be completed weekly for the duration of the home-use period. The StepWatch will be worn for approximately one month and then mailed back to the clinical site. At the end of the home-use period, subjects will return to the site for a follow-up visit for assessments (see Clinical Tests & Measures for test descriptions).

Clinical Tests & Measures

Data collection for the following clinical functional assessments will be collected on eCRFs. Several questionnaires and two performance based measures will be used in the study.

For an overview of the assessments required by visit, see Table 2.

Activity monitoring (daily step counts)

The StepWatch will be used for activity monitoring to collect daily step counts during the first month of each home-use period.

Six-minute walk test (6minWT)

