All training will be documented using training records including the elements of training completed, the trainers that delivered the training and the signatures of the participants. Site initiation visits or conference calls may be made by a Sponsor-appointed Monitor to review the Study Protocol and documentation requirements with the Investigator and clinic support staff involved in the study. The Sponsor will then determine if additional center-specific training is needed and will ensure that all researchers involved in the project have adequate training. Study activities may only be performed once the Sponsor confirms activation of the investigational site.

In addition to training, at a minimum, the following documentation must be in place at the investigational site before patient enrollment begins:

- Current Investigator's and Sub-Investigator's CVs
- Signed study agreement
- Completed training in human research subject protection or an overview of Good Clinical Practice if required by the IRB.
- IRB approval letter for the Study Protocol and amendment(s)
- Patient Informed Consent approved by both the IRB and Otto Bock Healthcare Products GmbH

Adverse Events

Adverse Event Definition

An adverse event is any untoward medical occurrence in a patient. An underlying disease or symptoms associated with the underlying disease that were present prior to the fitting of study devices are not reportable. However, any increase in severity of the underlying disease or symptoms since a study fitting is to be reported as an adverse event. If an adverse event leads to multiple outcomes that sequentially worsen during the course of the study, the worst event is reported. For example, skin irritation leading to a wound infection would be reported as infection.

Adverse Event Reporting

Once a subject is enrolled, all adverse events must be reported until the subject is withdrawn or is terminated from the study.

Adverse Event Adjudication

Events will be adjudicated per the definitions below.

Serious Adverse Event

A Serious Adverse Event (SAE) is an Adverse Event that:

1. led to a death;
2. led to a serious deterioration in the health of the patient that
 - results in a life-threatening illness or injury;
 - results in a permanent impairment of a body structure or a body function;
 - requires hospitalization or prolongation of existing hospitalization;

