 - results in medical or surgical intervention to prevent permanent impairment to body structure or a body function; or
3. led to fetal distress, fetal death or a congenital abnormality or birth defect.

Relatedness

Each adverse event will be assessed regarding relatedness to the study device or the fitting procedure. In addition, the level of relatedness will be classified according to definitions as presented in Table 3.

Table 3 Rating the Relatedness of Adverse Events

Relatedness:	Description:
Highly Probable	The adverse event follows a reasonable temporal sequence from receipt (or attempted receipt) of the device treatment or procedure.
Probable	The adverse event follows a reasonable temporal sequence from receipt of the device treatment or procedure and the possibilities of factors other than the device treatment or procedure, such as underlying disease, concomitant drugs, or concurrent treatment can be excluded.
Possible	The adverse event follows a reasonable temporal sequence from receipt of the device treatment or procedure and the possibility of device treatment or procedure involvement cannot be excluded. However, other factors such as underlying disease, concomitant medications, or concurrent treatment are presumable.
Unlikely	The adverse event has an improbable temporal sequence from receipt of the device treatment or procedure, or it can be reasonably explained by other factors, including underlying disease, concomitant medication, or concurrent treatment.
Not Related	The adverse event has no temporal sequence from receipt of the device treatment or procedure, or it can be explained by other factors, including underlying disease, concomitant medication, or concurrent treatment.

Severity Rating

The severity of adverse events will be classified according to definitions as presented in Table 4.

Table 4 Rating of the Severity of Adverse Events

Severity:	Description:
Mild	Usually transient, requiring no special treatment, does not interfere with the patient's daily activities.
Moderate	Low-level inconvenience or concern to the patient, may interfere with daily activities, usually resolved by simple therapeutic non-interventional methods.
Severe	Interruption in patient's daily activity requiring systemic drug therapy or other treatment.

Statistical Considerations and Data Analysis**Sample Size**

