Where H_0 is the null hypothesis, $\mu_{\text{Revo-M}}$ is the mean TAPES-FUN score using the Revo-M, μ_{Everyday} is the mean TAPES-FUN score using the everyday feet and H_A is the alternative hypothesis indicating that level of functional satisfaction as measured by the TAPES-FUN subscale is greater for Revo-M than for everyday feet.

The hypothesis will be tested using a 2-sided Wilcoxon matched pairs signed ranks test. If the observed p-value is \leq the Hochberg adjusted critical value and the mean of TAPES-FUN scores using the Revo-M foot is greater than TAPES-FUN scores using the everyday feet, the null hypothesis will be rejected in favor of the alternative hypothesis and the superiority of the Revo-M will be supported.

Exploratory Efficacy Endpoints

Although hypotheses have not been specified, statistical testing will be done using Wilcoxon's matched pairs signed ranks test comparing Revo-M to both comparative devices, the Taleo and the ProFlex, and comparing the Revo-M to the everyday foot (baseline at the end of Period I and crossover at the end of Period IV). However, as these objectives are exploratory in nature, any statistically significant differences will be considered to be hypothesis generating and not definitive. These results may be used to guide future studies with prosthetic feet.

Time Period

Data collection for all subjects will be collected from the time of enrollment until the end of Period IV. Patients may be given the opportunity to continue in Phase V for continued follow-up with the Revo-M for an additional 6 months.

Data Analysis

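### The worst-event reporting rule runs over the whole study, so an adverse event that worsens after a change of foot has no separate record under the foot on which it began

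*Combined protocol and SAP*

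**What the plan says.** The rule is in the protocol under Adverse Event Definition: "If an adverse event leads to multiple outcomes that sequentially worsen during the course of the study, the worst event is reported". The example that follows shows the milder stage being absorbed: "For example, skin irritation leading to a wound infection would be reported as infection".

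The study it spans is long and covers three feet. Under Time Period: "Data collection for all subjects will be collected from the time of enrollment until the end of Period IV". Under Period II – Period IV in the Study Summary: "After the first 8 week follow up, the subject will crossover to the second comparator", and then "After the second 8 week follow up, the subject will crossover to control". Table 2 places each fitting for the next period at Visits 2, 3 and 4, the same visits that close the preceding period. No washout is described.

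Under Relatedness: "Each adverse event will be assessed regarding relatedness to the study device or the fitting procedure". The safety objective reads: "To characterize all device-related adverse events, stumbles, and falls experienced by subjects in the study by frequency and severity".

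**The concern.** Merging a worsening chain into its worst stage is a reasonable convention when the subject wears one device throughout. Here the subject wears the everyday foot, two study feet in random order, and the everyday foot again. When a chain worsens step by step, the worst stage is the latest one. If a foot change falls between the stages, the single report describes the form the event took on the later foot, and the rule asks for no separate event under the foot on which it began.

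What is at stake is the reading of safety by device. The objective concerns device-related events by frequency and severity, and the Benefits section says that the safety of the Revo-M relative to the existing and comparative feet will be characterized. Both need some link between an event and a foot. If the earlier stage is not recorded at the time, with its date and foot, it cannot be reliably rebuilt at analysis.

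**Working it through.** The plan states no figure on this point, so there is nothing to reproduce. The check sets the relevant sections side by side and then counts.

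1. **Window of the rule.** Adverse Event Definition sets it as the course of the study. Time Period defines that as enrollment to the end of Period IV. It is not a period and not a foot.

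2. **Foot changes inside the window.** From Table 2 and the Randomization section:
   - Revo-M first: everyday to Revo-M (Visit 2), Revo-M to comparative (Visit 3), comparative to everyday (Visit 4).
   - Revo-M second: everyday to comparative (Visit 2), comparative to Revo-M (Visit 3), Revo-M to everyday (Visit 4).

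   Each completing subject has 3 changes. In both sequences 2 of the 3 involve the Revo-M, once when it is put on and once when it is taken off.

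3. **Any limit on the rule.** The sections on adverse event definition, reporting, relatedness, severity, the patient journal, the study periods and data analysis contain nothing that restarts the rule at a foot change, asks for the foot worn at onset, or says how a spanning event is dated. The sentences just before the rule use a study fitting as the reference point for worsening of underlying disease; the worst-event sentence does not.

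4. **Relatedness.** It is judged per reported event against the study device, although each subject wears two study devices in turn. In Table 3 the top category rests only on timing after receipt of the device. A worsened event soon after a new fitting could meet that wording for the new foot even if it began on the previous one.

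5. **Counting one case.** Take a mild event that starts on foot A and becomes severe on foot B.
   - Recorded by foot: 1 mild event on A and 1 severe event on B, linked.
   - Under the rule as written: 1 severe event, in the form it took on B, and no separate event on A.

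6. **Size of one case.** Sample Size gives a minimum of 24 subjects and a maximum of 30. One subject's contribution to the incidence on a foot that all subjects wear is 1/24 = 0.042, or 4.2 percentage points, at the minimum, and 1/30 = 0.033, or 3.3 points, at the maximum. This assumes that every enrolled subject wears the foot.

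7. **Expected number of cases.** This would need an adverse event rate and the chance that an event worsens after a foot change. The documents give neither, so it cannot be computed.

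**The case against.** Several counter-arguments have force.

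**The earlier stage may already be on a form.** Adverse Event Reporting requires every adverse event after enrollment to be reported until the subject leaves the study. Table 2 collects events at every visit, including those at which the foot is changed. Weekly journals are reviewed with the investigator, and adverse events found there go onto the Adverse Event form. Irritation noted in Period II should therefore be on a form by Visit 3. A reader might infer from the worst-event rule that the earlier event vanishes from the data; the documents do not establish that. Nor do they say whether the earlier form stands or is replaced once the event worsens. That gap remains.

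**No attribution is stated.** A reader might infer that the merged event is dated from, or charged to, the later foot. The text sets neither an onset date nor a foot. It treats the chain as one event with several outcomes, which could equally be dated from its start, and an assessor may still relate it to the earlier foot. Misattribution is thus a risk left open by silence, which sites may resolve differently, and not a stated rule.

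**The reach is narrow.** A reader might take every event that spans a visit to be affected. A stable or resolving event is untouched; only a chain that worsens after the change is caught. Unrelated events on different feet are still reported separately, and falls are entered in the journal in their own right.

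**No direction or percentage can be given.** A reader might infer that Revo-M events are understated, or put a percentage on the loss from an assumed event count. Shifts can go towards or away from the Revo-M, and any such count would be invented.

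**The objective is not worded per foot.** It covers events in the study as a whole, and Data Analysis specifies no by-foot comparison of events. The comparative intent is stated only under Benefits. This lowers the stakes but does not remove them: device-relatedness cannot be judged without knowing which device is meant.

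**The form's content is unknown.** The Adverse Event eCRF is listed by name only, so it may already capture onset date or device.

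**Conclusion.** The point holds as a defect in the recording rule. A convention suited to a single-device study is applied over a window with three foot changes, and nothing says how a chain that crosses one is kept, dated or attributed. The worst-event rule, the requirement to report all events and the journal route must be reconciled.

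The affected set is limited to chains that worsen after a foot change. The frequency of such chains is unknown and the direction of any bias is undetermined. One case is worth 4.2 to 3.3 percentage points of per-foot incidence with 24 to 30 subjects, if all of them wear the foot. No alpha, power or sample size figure is affected. It deserves correction because it touches the safety objective, is cheap to fix in advance, and is hard to repair afterwards.

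**What to change.** Limit the worst-event rule to the time during which the subject wears the same foot. Where an event worsens after a change of foot:

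- keep the original event with its onset date and the foot worn at onset;
- record the worsening as a linked event with its own date and foot;
- assess relatedness of each linked event against each foot worn;
- tabulate events by the foot worn at onset, and count a linked chain once in the overall total so that one clinical course is not counted twice.

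State also that a form completed before the foot change stands and is not replaced by the later report.

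The cost is a sentence or two in the protocol and, if the Adverse Event eCRF does not already hold them, fields for the foot worn and the linked event. The downside is that a few linked events appear twice in listings, which the link makes visible. The change concerns data recording only.
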